17.3. EARLY TERMINATION OF STUDY

The Sponsor may terminate this observational study at any time due to the following reasons, but not limited to: low subject recruitment/enrollment, competing studies and financial reasons. Appropriate notification will be provided to all participating Investigators.

18.DATA ANALYSIS

Study data will be analyzed as indicated in the Data Analysis Plan.

18.1. ELECTRONIC DATA COLLECTION

All study data will be collected using a database located on a secure server. Electronic CRFs will be utilized where possible. The study data will be reviewed by the Sponsor and queries will be generated to clarify data as necessary.

19.ADMINISTRATIVE RESPONSIBILITIES

19.1. INSTITUTIONAL REVIEW BOARD (IRB) APPROVAL

Principal Investigators must submit the study protocol to their respective IRB and obtain IRB written approval before being allowed to conduct the study. Each Principal Investigator must submit to the Sponsor a signed copy of the IRB approval letter, specific to this protocol and addressed to the Principal Investigator, certifying study approval prior to enrolling subjects into the study. The Principal Investigator is also responsible for fulfilling any conditions of approval imposed by their IRB, including maintaining continuation of the approval during the entire study period. The Principal Investigator will provide the Sponsor with copies of such approvals. The Principal Investigator must also keep on file all study-related correspondence with the IRB.

19.2. INFORMED CONSENT FORM (ICF) APPROVAL

The Sponsor will provide a template ICF to each site for IRB submission prior to site initiation. This template may be modified to suit the requirements of the individual study site. The Sponsor must

pre-approve all changes to the ICF prior to initial submission to the IRB. A copy of the original IRB-approved ICF must be sent to the Sponsor prior to study start while the original must be retained at the study site. If the ICF is amended by the reviewing IRB, a copy of the approved document must be provided to the Sponsor prior to enrollment of subjects in the study.

The Investigator or authorized designee must administer the approved ICF to each prospective study subject. Informed consent must be obtained in accordance with the applicable guidelines of 21 CFR Part 50 and local laws and regulations, whichever represents the greater protection of the individual.

This study will be registered on http://www.ClinicalTrials.gov. The following statement will be included in the ICF for the study to notify the prospective subjects for the study: "A description of this clinical trial will be available on http://www.ClinicalTrials.gov, as required by U.S. Law. This Web site will not include information that can identify you. At most, the website will include a summary of the results. You can search this website at any time."

19.3. CONFIDENTIALITY

All information and data sent to the Sponsor concerning subjects or their participation in this study will be considered confidential. All data used in the analysis and reporting of this data will be used in a manner without identifiable reference to the subject. The Investigator consents to visits by the Sponsor or designee and authorized governmental body to review the study subjects' medical records, including any test or laboratory data that may have been recorded on diagnostic test media (e.g., angiogram).

19.4. SPONSOR RESPONSIBILITIES

Sponsor responsibilities include but are not limited to:

- Selection of Principal Investigators, study sites, and Core Laboratories who participate in the study;
- Training of participating study sites including the Investigator and staff conducting the study;
- Providing financial support to each study site which is fair, reasonable, and equitable to fair market value;
- Following/promoting all applicable regulatory standards per applicable regulations at each study site; and,
- Ownership and control of the use of data, including review and approval of study-related publications/presentations, etc.

19.5. INVESTIGATOR RESPONSIBILITIES

The Investigator is responsible for the following:

- Protecting the rights, safety, and welfare of subjects.
- Conducting the investigation in accordance with the Clinical Trial Agreement with the Sponsor, the Protocol, applicable FDA regulations, including 21 CFR Part 50 and 56, and any conditions of approval imposed by the IRB.
- Delegation of study-related tasks to qualified personnel under their supervision as may be applicable; however, the Principal Investigator remains responsible for the proper conduct of the clinical study.
- Enrollment will commence when the Sponsor has received all required documentation, including but not limited to the signed Clinical Trial Agreement and IRB approvals.
- At each site, appropriate procedures must be followed to maintain subject confidentiality according to the Health Insurance Portability and Accountability Act (HIPAA) regulations. Each site may have its own internal procedures or requirements for use and release of subject medical information in research studies. Each Investigator is responsible for obtaining

- appropriate approvals, consents, or releases of medical information as dictated by their site's relevant patient privacy laws.
- The study is not transferable to other sites attended by the Principal Investigator unless prior approval is obtained from the appropriate IRB and the Sponsor.
- It is recommended that all records pertaining to this study will be kept for a minimum of two (2) years following the date on which the study is completed or terminated.

20.INVESTIGATOR RECORDS AND REPORTS

20.1. INVESTIGATOR RECORDS

Investigator is responsible for preparing and/or retaining the following records:

- Subject's case history records, including: signed/dated ICF, observations of adverse events, relevant medical history, results of tests and/or exams performed in this study, and dates and data collected at office visits and telephone follow-up;
- · Protocol and any amendments; and
- IRB approval documents and related correspondence.

2 INTRODUCTION

The Data Analysis Plan (DAP) is designed to pre-define analysis and assist in the analysis of the data collected in LIBERTY study. This plan includes a description of the study objectives and endpoints listed in the LIBERTY study protocol . This DAP should be read in conjunction with the study protocol and electronic Case Report Forms (eCRF). This version of the plan has been developed with respect to the LIBERTY 360 protocol . Any changes to the protocol or eCRFs may necessitate updates to the DAP.

CONFIDENTIAL

3 LIBERTY STUDY DESIGN

The LIBERTY 360° is a prospective, observational, multi-center, clinical study examining the predictors of clinical outcomes for patients undergoing endovascular treatment of lesions within or extending into the target area (10 cm above the medial epicondyle to the digital arteries). This includes disease in the distal superficial femoral artery (SFA), popliteal (POP), tibial peroneal trunk (TPT), anterior tibial (AT), posterior tibial (PT), and peroneal tibial (PR) arteries.

3.1 Study Objectives

The objectives of LIBERTY study are:

Evaluate procedural and long-term clinical and economic outcomes for subjects
undergoing peripheral endovascular device intervention used to treat lower extremity
PAD that includes a target lesion located in a native vessel located within or extending
into the target area (10 cm above the medial epicondyle to the digital arteries). This
includes disease in the distal SFA, POP, TPT, AT, PT, and PR arteries.

3.2 Patient Selection

Subjects must meet ALL of the inclusion criteria and NONE of the exclusion criteria as outlined in the LIBERTY study protocol to be eligible to participate in this study. For a complete list of criteria refer to the study protocol.

3.3 Sample Size

Approximately 1,200 subjects will be enrolled in this study. The study cohort will be divided into three study arms according to the most severe clinical syndrome present at the time of study enrollment:

- "Claudicant" Arm (Rutherford 2-3) 500 subjects
- "CLI Rutherford 4-5" Arm 600 subjects
- "CLI Rutherford 6" Arm 100 subjects

The analysis of data for the LIBERTY study will be based on the objectives outlined in the protocol. Analyses will be conducted on locked clinical study data using SAS software (S Institute, Inc., [name]). In the event an analysis is required is better suited for a statistical package other than SAS, this other package (e.g. R) will be used.
For all analyses, Rutherford category will be defined as each study arm. These will be used as
basis for comparisons of treatment and treatment location as well as clinical and economic outc within the study arm. The primary and secondary specific analyses for descriptive purposes and
planned outcome analyses will be performed as pre-specified in this analysis plan.

Baseline patient characteristics and risk factors will be presented by study arm. This will include frequency distributions for categorical variables and summary statistics for continuous variables as

CONFIDENTIAL	
LIBERTY 360 Data Analysis Plan	Page 6

n	17	11	**	2	n	***	O.	te
7			ш	•	.,		7	
•	r	М	-	~	Μ.			•
	•	•		_	٠.		-	

5.1 Procedure and Long-Term Clinical and Economic Outcomes (Study Objective #1)

Procedure and long-term clinical and economic outcomes include lesion success, procedural success, clinical outcomes , major adverse event rates, and economic outcomes. Treatment outcomes at a minimum will be summarized overall and by treatment group. The statistical approach to assess these outcomes is described above.

5.1.1. Endpoint 1: Procedural and Lesion Success

Procedural success is defined as a final post-procedural result of < 50% residual stenosis for all treated lesions during index procedure and without significant angiographic complications (perforation, dissection type C-F, distal embolization, acute vessel closure) as determined by the Angiographic Core Laboratory.

Lesion success is defined as a final post-procedural result of < 50% residual stenosis for a given lesion treated during index procedure and without significant angiographic complications as determined by the Angiographic Core Laboratory.

The rates of procedural success and of lesion success will be estimated in the context of a logistic regression, and will attempt to quantify the relationship between covariates or sub-group effects and success rates.

[figure not shown]

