1. ABBREVIATIONS

ABI	Ankle Brachial Index	
AE	Adverse Event	
AT	Anterior Tibial	
BA	Balloon Angioplasty	
CFR	Code of Federal Regulations	
CLI	Critical Limb Ischemia	
CSI	Cardiovascular Systems, Inc.	
eCRF	Electronic Case Report Form	
EDC	Electronic Data Capture	
FDA	Food and Drug Administration	
HIPAA	Health Insurance Portability and Accountability Act	
IC	Intermittent Claudication	
ICF	Informed Consent Form	
IFU	Instructions for Use	
IRB	Institutional Review Board	
MAE	Major Adverse Event	
LER	Lower Extremity Revascularization	
OAS	Orbital Atherectomy System	
PAD	Peripheral Artery Disease	
PI	Principal Investigator	
POBA	Plain Old Balloon Angioplasty	
POP	Popliteal	
PPG	Photoplethysmography	
PR	Peroneal Tibial	
PT	Posterior Tibial	
PTA	Percutaneous Transluminal Angioplasty	
SFA	Superficial Femoral Artery	
ТВІ	Toe Brachial Index	
TLR	Target Lesion Revascularization	
TVR	Target Vessel Revascularization	
TPT	Tibial Peroneal Trunk	
US	United States	

2. **DEFINITIONS**

Term	Definition	
Dissection classification ¹	Type 0: None Type A: Small radiolucent area within lumen of the vessel Type B: Linear, non-persisting extravasation of contrast Type C: Extraluminal, persisting extravasation of contrast Type D: Spiral shaped filling defect Type E: Persistent lumen defect with delayed ante/retrograde flow Type F: Filling defect accompanied by total arterial occlusion Note: Type A and B are generally considered benign and minor dissections.	
Digital arteries	Arteries that are the collateral digital branches of the dorsal metatarsal arteries in the foot.	
Outflow	Arterial flow to the foot starting from tibial vessels (AT, TPT, PT, and PR arteries).	
Inflow	For the LIBERTY study, inflow treatment on the target limb is defined as treatment located entirely above the protocol defined target area, not inclusive of any lesion that extends into the target area, as defined by the LIBERTY protocol.	
Lesion success (per lesion)	A final post-procedural result of < 50% residual stenosis for a given target lesion treated during index procedure as determined by the Angiographic Core Laboratory without significant angiographic complications.	
Major adverse events (MAEs)	Death within 30 days of index procedure, unplanned major (above ankle) amputation of index limb, clinically-driven target lesion revascularization (TLR) or target vessel revascularization (TVR) of the index limb.	

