Procedural success (per subject)	A final post-procedural result of < 50% residual stenosis for all treated target lesions during index procedure without significant angiographic complications, as determined by the Angiographic Core Laboratory.	
Rutherford classification ²	Class 0: Asymptomatic; no hemodynamically significant occlusive disease. Class 1: Mild Claudication; there is no limitation with ordinary physical activities (e.g., walking several blocks, climbing stairs). Limiting symptoms may occur with marked exertion (e.g., strenuous, rapid or prolonged exertion at work or recreation). Class 2: Moderate Claudication; there is a slight limitation of ordinary physical activities (e.g., walking uphill, or more than two level blocks, or climbing stairs rapidly). Patient is comfortable at rest. Class 3: Severe Claudication; there is marked limitation of ordinary physical activities (e.g., walking 1-2 level blocks or climbing one flight of stairs). Patient is comfortable at rest. Class 4: Ischemic rest pain. Class 5: Minor tissue loss, non-healing ulcer, focal gangrene with diffuse pedal ischemia. Class 6: Major tissue loss extending above transmetatarsal level; functional foot no longer salvageable.	
Significant Angiographic complications	Perforation, dissection type C-F, distal embolization, acute vessel closure that occurred during index treatment of target lesion(s).	
Target area	An area located within or extending into10 cm above the medial epicondyle to the digital arteries.	
Target lesion(s)	Stenotic segment(s) within or extending into the target area treated with an endovascular device(s) during the index procedure.	
Target lesion revascularization (TLR)	Repeat revascularization of the target lesion(s) includes:	

Term	Definition
Target vessel revascularization (TVR)	Repeat revascularization of the target vessel(s) (exclusive of the target lesion) includes: PTA Stenting Atherectomy Bypass graft Other treatments

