5.2. STATISTICAL METHODOLOGY

This observational study will analyze the outcome measures based on outlined endpoints. The study data will be reported using descriptive analysis.

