6.2. SUBJECT ENROLLMENT

The subject will be considered enrolled in the study when:

- He/she signs an informed consent form (ICF);
- All of the inclusion and none of the exclusion criteria are met; and,
- At least one lesion in the target area of a native vessel is treated with an endovascular device.
 - Note: a) at least one target lesion must be crossed and treated for subject to be considered enrolled in the study.
 - b) if during index procedure, endovascular treatment of the target lesion is converted to bypass, subject is not considered enrolled in the study, therefore no study follow-up is needed.

All efforts will be made to ensure that consecutive subjects are being included in the study. The subject's treatment method(s) will be determined by the treating Investigator. Assignment to study arms will be based upon Rutherford classification at baseline

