6.4. INCLUSION CRITERIA

- 1. Subject's age \geq 18 years.
- 2. Subject presents with a Rutherford classification of 2 to 6.
- 3. Subject presents with clinical evidence of PAD requiring endovascular intervention on one or both limbs that includes a target lesion in a native vessel located within or extending into 10

cm above the medial epicondyle to the digital arteries.

- o If subject presents with bilateral disease, the first limb treated with a lesion in the target area will be considered the target limb.
- For subjects with one or more wounds on the target limb, the target lesion(s) should be considered the lesion(s) in the vessel(s) that provide(s) blood flow to the wound(s).
- 4. Subject has at least one lesion in a native vessel located within or extending into the target area that is crossed and treated with an endovascular device.

Note: the Investigator can make an additional attempt to treat a lesion in the target area at a later time point if the initial attempt to treat was unsuccessful. If successful on reintervention, the subject can be enrolled.

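### SAP 5.1.1 names logistic regression for a per-subject and a per-lesion outcome, and the public text does not say how several target lesions in one subject are handled.

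*SAP*

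**What the plan says.** SAP 5.1.1 covers both parts of Endpoint 1 in one sentence: "The rates of procedural success and of lesion success will be estimated in the context of a logistic regression". The model is also meant to relate success to covariates and sub-groups.

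The two outcomes have different units. Protocol section 2 defines "Procedural success (per subject"), which requires a good result "for all treated target lesions during index procedure", and "Lesion success (per lesion"), which is judged one lesion at a time. A subject can contribute more than one lesion. Protocol 6.2 sets only a minimum ("at least one target lesion must be crossed and treated for subject to be considered enrolled in the study"), Protocol 6.4 criterion 3 allows several target lesions where there are wounds, and no maximum is given.

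On use of the results, Protocol 5.2 says "The study data will be reported using descriptive analysis". The analysis text that follows SAP 3.3 makes study arm the "basis for comparisons of treatment and treatment location as well as clinical and economic outc within the study arm" (the public copy is damaged here). SAP 5.3 applies a two-sided 0.05 level to all tests and intervals and asks for SD, SE or confidence intervals with findings.

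No public passage names GEE, a random effect, a cluster-robust variance or a one-lesion-per-subject rule. SAP 5.1 refers back to a statistical approach given earlier, but the text before it breaks off. No section 4, 5.2 or 5.4 is visible, and a figure is missing after the text of 5.1.1.

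**The concern.** An ordinary logistic fit counts every row as independent information. That suits procedural success, with one row per subject. It need not suit lesion success, because lesions in one subject share the patient, the operator and the procedure. If their outcomes are positively correlated, an independence fit overstates the information in the data. Intervals for lesion success rates come out too narrow, and covariates that are constant within a subject are declared significant too often.

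Lesion success is half of Endpoint 1, and SAP 5.3 makes lesion-level intervals and p-values foreseeable outputs. If the method is not fixed in advance, it may be chosen after the data are seen.

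**Working it through.** **1. Plan figures.** The documents state no power, precision or event figure that depends on this point, so there is nothing to reproduce. The arm sizes in SAP 3.3 add up: 500 + 600 + 100 = 1,200.

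**2. Inputs.** From the documents: two-sided alpha 0.05 (SAP 5.3) and arm sizes (SAP 3.3). Assumed, because the documents give none of them: the distribution of lesions per subject, the ICC, and an 85% success rate where a rate is needed.

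**3. Formulas.** With m lesions per subject:

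- design effect DE = 1 + (E[m²]/E[m] − 1) × ICC
- actual alpha = 2 × (1 − Φ(1.96/√DE)), for a subject-level covariate
- widening of the correct interval = √DE − 1

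Middle case in full, with 65/25/8/2% of subjects having 1/2/3/4 lesions:

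- E[m] = 0.65 + 0.50 + 0.24 + 0.08 = 1.47
- E[m²] = 0.65 + 1.00 + 0.72 + 0.32 = 2.69
- DE = 1 + (2.69/1.47 − 1) × 0.3 = 1.249
- 1.96/√1.249 = 1.754, so actual alpha is 7.9%

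| Subjects with 1/2/3/4 lesions (%) | Mean | ICC | DE | Actual alpha | Interval widening |
|---|---|---|---|---|---|
| 95/5/0/0 | 1.05 | 0.1 | 1.010 | 5.1% | 0.5% |
| 95/5/0/0 | 1.05 | 0.5 | 1.048 | 5.6% | 2.4% |
| 80/15/4/1 | 1.26 | 0.1 | 1.052 | 5.6% | 2.6% |
| 65/25/8/2 | 1.47 | 0.3 | 1.249 | 7.9% | 11.8% |
| 40/35/17/8 | 1.93 | 0.5 | 1.694 | 13.2% | 30.2% |

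**4. Rutherford 6 arm.** 100 subjects at mean 1.47 give 147 lesions. At 85% success the naive half-width is 1.96 × √(0.85 × 0.15/147) = 5.8 points. Multiplied by √1.249 it is 6.5 points.

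**5. Simulation, subject-level factor.** Settings: beta-binomial lesion outcomes, 85% success, the last three lesion distributions, ICC 0.1, 0.3 and 0.5, and 10,000 replicates per cell (Monte Carlo SE about 0.22 points at 5%).

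| Subjects | Fit | Type I error | Coverage of 95% interval for overall rate |
|---|---|---|---|
| 600 | Independent lesions | 5.3% to 14.0% | 94.5% down to 86.8% |
| 600 | Independence GEE, robust SE | 4.6% to 5.3% | 94.8% to 95.4% |
| 100 | Independent lesions | 4.6% to 12.0% | 94.7% down to 86.5% |
| 100 | Independence GEE, robust SE | 4.1% to 5.6% | 94.5% to 95.3% |

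In a separate simulation at 100 subjects, a plain Wald robust interval covered 93.2% to 93.9%, against 85.7% to 93.4% for the naive one. Robust intervals can therefore fall slightly short in the smallest arm.

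**6. Unbalanced covariate in a small arm.** With 100 subjects, mean 1.47 and ICC 0.3, the naive type I error is 7.3% for a 50/50 subject-level covariate but 5.1% for a 20/80 split.

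**7. Factors that vary between lesions.** Naive type I error with 600 subjects, 85% success and 6,000 replicates:

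| Pattern of the factor | Mean 1.47, ICC 0.3 | Mean 1.93, ICC 0.5 |
|---|---|---|
| Alternates between a subject's lesions | 3.3% | 1.8% |
| Assigned independently to each lesion | 4.8% | 5.4% |

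The test is conservative when the factor is balanced within subjects and near nominal when it is unrelated to subject.

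**The case against.** The strongest objection is that the gap lies where text is missing. SAP 5.1 points to an approach described earlier, and that part of the public copy is broken. A reader might infer that the SAP has no method for clustered lesions. The documents do not support that; they support only the statement that no method is visible. A reader might also infer that lesions will be analysed as independent. The SAP does not say so, and a logistic GEE or random-intercept model would also fit its wording. This part of the objection stands, and it is why the point is conditional.

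Second, the consequences are modest. Reporting is descriptive, and no visible hypothesis or decision depends on a lesion-level p-value. That stands as a limit on severity. It does not remove the point, because SAP 5.3 still asks for measures of precision and sets a threshold for significance.

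Third, every size is assumed, and the effect is near nil if almost all subjects have one lesion. That stands.

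Fourth, a reader might infer that comparisons of treatment location would be too conservative. That holds only if location is balanced within subjects, and the documents do not say how location is coded or whether it varies within a subject.

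Fifth, clustering by subject does not cover correlation within operator or site, although Protocol 6.1 allows up to 100 sites. That is fair. Subject-level clustering addresses only the repeated lesions at issue here, and independence GEE is one defensible choice among several.

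**Conclusion.** The point holds in conditional form. The public SAP names one model for two units of analysis and shows no provision for several lesions in one subject. If lesions are fitted as independent and their outcomes are positively correlated, which is plausible but not documented, lesion-level intervals are too narrow and tests of subject-level covariates are generally too liberal. Actual alpha is about 5.1% (95% of subjects with one lesion, ICC 0.1) to 13.2% (mean 1.93, ICC 0.5), with less inflation in small arms when the covariate is unbalanced. For factors that vary between lesions, the direction depends on their pattern, and no general bias can be claimed.

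Observed lesion percentages are unaffected. So is procedural success, which has one result per subject. The harm is confined to standard errors, intervals and p-values for lesion success. This is worth settling before analysis, but it does not threaten the study's main descriptive results.

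**What to change.** In SAP 5.1.1, keep subject-level logistic regression for procedural success. For lesion success, specify logistic regression with subject as the cluster and robust standard errors, and report cluster-robust intervals for lesion-level rates. One suitable form is GEE with an independence working correlation, which gives the same rates and odds ratios as the plain fit, so modelled rates still match the raw lesion percentages. An exchangeable structure reweights lesions and need not match. In an illustration with assumed success of 88/84/78% for subjects with 1/2/3+ lesions, the raw and independence-GEE rates were both 84.4% and the exchangeable rate was 85.4% (600 subjects, mean 1.47, ICC 0.3, 30 replicates). If the non-public text already specifies a clustered method, a cross-reference in 5.1.1 is enough.

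The cost is one sentence and one procedure call in SAS, the planned software (PROC GENMOD with REPEATED SUBJECT= and TYPE=IND). No new data are needed. Intervals for lesion-level rates widen by about 3% (mean 1.26, ICC 0.1) to 30% (mean 1.93, ICC 0.5), and independence GEE can be less efficient than an exchangeable structure for within-subject factors.
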